### 7.2. Lost to Follow-up

A subject will be considered lost to follow-up if he or she repeatedly fails to return for scheduled visits and is unable to be contacted by the study center.

Before a subject is deemed lost-to-follow-up, the study center should make every effort to contact the subject (see Section 7.1) and reschedule the missed visit as soon as possible. The subject should be counseled on the importance of visit compliance and should be questioned as to whether he or she wishes to continue in the study.

## 8. Study Assessments and Procedures

### 8.1. Subject Entry Procedures

Subject informed consent must be obtained prior to conducting screening procedures. Each signature must be personally dated by each signatory and the original retained by the PI as part of the study record. A signed copy must be provided to each subject (refer to Section 5.3).

### 8.2. Schedule of Visits and Procedures

It is recommended that study visits be scheduled at approximately the same time of day throughout the trial. The IGA-FHWS, IGA-FWS, and Investigator GAIS should be performed by the same evaluator throughout the study. If it is not possible to use the same evaluator throughout the study, two evaluators should examine the subject together and discuss findings for at least 1 prior visit. The SOA is provided in Section 1.3.

#### 8.2.1. Screening Visit

The Screening Visit must take place within 14 days prior to the GL treatment visit (Day 1 Visit).

The following procedures must be performed and recorded at this visit:

[figure not shown]
1. Review study procedures and information regarding the trial and obtain written informed consent and privacy authorization (as applicable)
2. Review eligibility criteria
3. Obtain medical/surgical history, including prior toxin use, and demographic information, including Fitzpatrick skin phototype
4. Once the investigator has confirmed eligibility criteria, the subject will be enrolled

8. Perform a physical examination,
10. Measure and record vital signs (body temperature, respiratory rate, sitting radial pulse, and sitting systolic and diastolic blood pressure); subjects should sit for 5 minutes prior to taking pulse and blood pressure

12. Collect blood and urine samples for clinical safety laboratory tests (hematology, serum chemistry, PT, and urinalysis)

14. Conduct patient education: Discuss the potential effect of DAXI for injection treatment, explain the PFWS and PFHWS measurement and the categories of the severity assessment scales, and instruct the subjects to consider depth of lines for GL and FHL severity. Use the provided Patient Education Brochure

The Screening Visit clinical laboratory test results and UPT must be reviewed and signed by the investigator; any abnormal results must be determined to be not clinically significant by the investigator prior to enrollment.

### **8.2.2. Treatment Visits (Day 1 and Week 2)**

The GL Treatment Visit (Day 1 Visit) must be performed within 14 days of the Screening Visit. The FHL Treatment Visit will occur at the Week 2 Visit. The following procedures must be performed and recorded for each visit:

#### **Prior to Investigational Product Administration**

1. Confirm that all screening visit procedures have been completed, results reviewed, and recorded (Day 1 Visit only)
2. Review eligibility criteria
3. Update medical/surgical history (Day 1 Visit only)
4. Once the investigator has confirmed subject eligibility, enroll the subject (Day 1 Visit only)

17. Measure and record vital signs (body temperature, respiratory rate, sitting radial pulse, and sitting systolic and diastolic blood pressure); subjects should sit for 5 minutes prior to taking pulse and blood pressure

20. Conduct patient education for GL and FHL evaluation: Discuss the potential effect of DAXI for injection treatment, explain the PFWS and PFHWS measurement and the categories of the severity assessment scales, and instruct the subjects to consider depth of lines for GL and FHL severity. Use the provided Patient Education Brochure

23. Record concomitant therapy/medications at the Screening Visit (and in the 30 days prior to screening) documenting the dose and dosing regimen of all prescription and non-prescription therapies and medications, including herbs, vitamins, or other nutritional supplements (Section 6.3).

## Investigational Product Preparation

The assigned investigational product will be prepared by the trained dose preparer according to trial-specific instructions. The prepared investigational product will be provided in a syringe to the Investigator for administration.

## Investigational Product Administration

Investigational product will be administered by the Investigator to injection site in the designated treatment area (Refer to Section 6.2.4) while the subject is in a sitting position.

1. Wear protective gloves for investigational product administration.

2. Pull subject's hair away from the treatment area.
3. Wipe all injection sites with alcohol.

#### **After Investigational Product Administration**

obtain vital signs (body temperature, respiratory rate, sitting radial pulse, and sitting systolic and diastolic blood pressures)

#### **8.2.3. Week 1 and 3 Follow-Up Phone Call**

At the Week 1 and 3 follow-up phone call, the subject will be contacted by the site staff for a health status check, concomitant therapy/medication check, and a query about AEs that may have occurred.

The following procedures must be performed and recorded:

2. Query subject about any new or ongoing AEs since the last visit
3. Query subject about concomitant therapy/medication

#### 8.2.4. Follow-up Visits

At Weeks 4, 6, 10, 14, 18, 22, 26, 30, and 34 the following procedures must be performed and recorded:

10. Collect blood and urine samples for clinical safety laboratory tests (hematology, serum chemistry, and urinalysis) (Week 4 Visit only)

12. Conduct patient education for GL and FHL evaluation: discuss the potential effect of DAXI for injection treatment, explain the PFWS and PFHWS measurement and the categories of the severity assessment scales, and instruct the subjects to consider depth of lines for severity of their GL and FHL. Use the provided Patient Education Brochure

16. Assess any new or ongoing AEs since the last visit

### 8.2.5. Final Evaluation Visit (Week 38)

The following procedures must be performed and recorded at the Final Evaluation Visit for each subject. Following treatment, subjects will be followed for at least 24 weeks from GL treatment for safety or until all scores on the IGA-FWS and PFWS, as well as the IGA-FHWS and PFHWS return to baseline (Day 1 Visit) or until Week 38, whichever occurs first. Subjects will then have a Final Evaluation Visit at which time the following procedures must be performed and recorded:

8. Perform a physical examination

(hematology, serum chemistry, and urinalysis)

13. Conduct patient education for GL and FHL evaluation: Discuss the potential effect of DAXI for injection treatment, explain the PFWS measurement and the categories

of the severity assessment scales, and instruct the subjects to consider depth of lines for severity of their glabellar lines. Use the provided Patient Education Brochure

[REDACTED]

[REDACTED]

[REDACTED]

16. Assess for any new or ongoing AEs since the last visit

[REDACTED]

[REDACTED]

If there are no safety concerns, the subject's participation in the study is complete at this visit.

### **8.2.6. Variation from Scheduled Visit Days**

To allow for scheduling flexibility, limited variation will be permitted from the specified time of each visit (Table 3).

**Table 3: Allowed Variation from Scheduled Visit Days**

Scheduled Visit	Allowed Variation
Weeks 1, 2, and 3	+ 2 days
Weeks 4, 6, 10, 14, 18, 22, 26, 30, 34, and 38	+/- 4 days

## **8.3. Efficacy Assessments**

Effectiveness assessments will include investigator assessment of GL and FHL severity and improvement on the IGA-FWS and IGA-FHWS, as well as subject assessment of severity and improvement on the PFWS and PFHWS. Effectiveness assessments will be conducted with the subject in a sitting position. To ensure consistent eye positioning during the assessment, the investigator should ask the subject to focus on a fixed point in the examination room. The assessment should be conducted in a room with good overhead lighting or natural light from a window (but not direct sunlight). Investigator assessments of improvement should be performed by the same evaluator throughout the study for a given subject. (Refer to Section 8.2.)

### **8.3.1. Investigator Global Assessment Frown Wrinkle Severity**

At each clinic visit as designated in the SOA (Section 1.3), the investigator will assess the visual appearance (at rest and at maximum frown) of the GL using the IGA-FWS with the following 4-point scale (Table 4).

**Table 4: Investigator Global Assessment Facial Wrinkle Severity (IGA-FWS)**

Rating Score	Frown Wrinkle Severity	Description
0	None	No wrinkles
1	Mild	Very shallow wrinkles
2	Moderate	Moderate wrinkles
3	Severe	Deep and furrowed wrinkles

### 8.3.2. Investigator Global Assessment Forehead Wrinkle Severity

At each clinic visit as designated in the SOA (Section 1.3), the investigator will assess the visual appearance (at rest and at maximum eyebrow elevation) of the FHL using the IGA-FHWS with the following 4-point scale (Table 5).

**Table 5: Investigator Global Assessment Forehead Wrinkle Severity (IGA-FHWS)**

Rating Score	Forehead Wrinkle Severity	Description	
		At Rest	At Maximum Eyebrow Elevation
0	None	No horizontal forehead lines	None to minimally visible horizontal forehead line(s)
1	Mild	Barely visible, shallow horizontal forehead line(s)	Visible, shallow horizontal forehead line(s)
2	Moderate	Clearly visible, moderate depth horizontal forehead line(s)	Clearly visible, moderate depth horizontal forehead line(s)
3	Severe	Clearly visible, deep horizontal forehead line(s) with redundancy of skin	Clearly visible, deep horizontal forehead line(s) with redundancy of skin

### 8.3.3. Patient Frown Wrinkle Severity (PFWS)

Subjects will complete the Patient Frown Wrinkle Severity (PFWS) assessment (at rest and at maximum frown) to assess the severity of the GL at the Screening Visit, Treatment Visit pre-treatment, Follow-up Visits, and Final Evaluation Visit.

The subject assessment form will be provided directly to the subject to complete while reviewing their GL treated area using the supplied handheld mirror. Refer to Appendix 6 for additional information.

**Table 6: Patient Frown Wrinkle Severity (PFWS)**

Rating Score	Frown Wrinkle Severity	Description
0	None	No wrinkles
1	Mild	Very shallow wrinkles
2	Moderate	Moderate wrinkles
3	Severe	Deep wrinkles

### 8.3.4. Patient Forehead Wrinkle Severity (PFHWS)

At each clinic visit as designated in the SOA (Section 1.3), the subject will assess the visual appearance of FHL using the PFHWS (at rest and at maximum eyebrow elevation). The assessment form will be provided directly to the subject to complete while reviewing the treatment areas using the supplied handheld mirror. Subjects who wear contact lenses should view the treatment areas while wearing their contact lenses. Subjects who wear glasses must have sufficient visual acuity to view the treatment areas without glasses. The subject assessment must be completed before the investigator completes the IGA-FHWS assessment. Refer to Appendix 7 for additional information.

**Table 7: Patient Forehead Wrinkle Severity (PFHWS)**

Rating Score	Forehead Wrinkle Severity	Description	
		At Rest	At Maximum Eyebrow Elevation
0	None	No horizontal forehead lines	None to minimally visible horizontal forehead line(s)
1	Mild	Barely visible, shallow horizontal forehead line(s)	Visible, shallow horizontal forehead line(s)
2	Moderate	Clearly visible, moderate depth horizontal forehead line(s)	Clearly visible, moderate depth horizontal forehead line(s)
3	Severe	Clearly visible, deep horizontal forehead line(s) with redundancy of skin	Clearly visible, deep horizontal forehead line(s) with redundancy of skin

The assessment will represent wrinkle severity at each given time point and will not be based on a comparison to the pre-treatment defect level. It is recommended that visit assessments be completed by the subject as close to the same time of day as possible.

### **8.3.5. Global Aesthetic Improvement Scale (GAIS)**

The investigator and subject will assess the visual appearance (at maximum eyebrow elevation) of the improvement from the baseline condition in FHL and in visual appearance in the improvement of GL during maximum frown using the following 7-point severity GAIS (Table 8). Subjects will use the baseline assessment photograph for comparison when reviewing the visual appearance for GL and FHL to assess improvement following treatment. Assessments will be made as designated in the SOA (Section 1.3).

The Patient GAIS assessment form (Appendix 5) will be provided directly to the subject to complete while reviewing the glabellar treatment area (at maximum eyebrow elevation and maximum frown) using the supplied handheld mirror as outlined in Appendix 5. Subjects who wear contact lenses should view their treatment area while wearing their contact lenses. Subjects who wear glasses must have sufficient visual acuity to view their treatment area without glasses. The subject assessment must be completed before the investigator completes the IGA-FWS and IGA-FHWS assessment.

**Table 8: Global Aesthetic Improvement Scale**

[figure not shown]
Rating Score	Wrinkle Improvement
-3	Very Much Worse
-2	Much Worse
-1	Worse
0	No Change
1	Improved
2	Much Improved
3	Very Much Improved

### 8.3.6. Facial Age Self Evaluation (FASE)

At each clinic visit designated in the SOA (Section 1.3), the subject will be asked to rate their perceived age on a FASE questionnaire (Appendix 9). Following the subject's completion of the Patient GAIS, the subject will be given a questionnaire to rate their perception of how old they think they look following the treatment.

### 8.3.7. FACE-Q™

At each clinic visit designated in the SOA (Section 1.3), the subject will be asked to complete the FACE-Q™ Satisfaction with Forehead and Eyebrows and the FACE-Q™ Appraisal of Lines: Forehead questionnaires (Appendix 11). The questionnaires ask subjects to rate how bothered they are by their FHL using 7 questions about general appearance with a rating scale of 1 to 4 with 1 representing Not Bothered and 4 representing Extremely Bothered. Refer to Appendix 11 for additional information.

[REDACTED]

[REDACTED]

[REDACTED]

[REDACTED]

[REDACTED]

[REDACTED]

#### ***8.3.9.1.2. Subject Global Satisfaction with Treatment Questionnaire***

At each clinic visit designated in the SOA (Section 1.3), the subject will be asked to provide a rating of their satisfaction with the treatment results. Following the subject's completion of the Patient GAIS, the subject will be given the Subject Global Satisfaction with Treatment Questionnaire to rate their satisfaction with the treatment results. Subjects will be asked how satisfied or dissatisfied they are with how the treated area of the face looks (Appendix 10).

### **8.4. Safety Assessments**

Planned time points for all safety assessments are provided in the SOA (Section 1.3).

#### **8.4.1. Physical Examination**

A targeted physical examination, [REDACTED], will be conducted at the Screening Visit and at the Day 1, Week 2 and Final Evaluation Visits. Significant physical examination findings that are present prior to investigational product administration are to be included on the Medical History eCRF.

Significant physical examination findings after investigational product administration which meet the definition of an AE will be recorded on the AE eCRF.

#### **8.4.2. Vital Signs**

Vital signs (i.e., body temperature, respiration rate, sitting radial pulse rate, and sitting systolic and diastolic blood pressures) will be obtained at the Screening Visit and at the Day 1 and Week 2 and 38 Visits, or Final Evaluation Visit, [REDACTED] [REDACTED]. New abnormal findings or worsening from baseline (Day 1 prior to GL treatment) at subsequent assessments, if judged clinically significant, should be recorded as an AE.

#### **8.4.3. Pregnancy Testing**

A UPT is required for all WOCBP at screening and a UPT is required at the Screening Visit and at the Day 1 (pre-treatment), Week 2 and 38 Visits or Final Evaluation Visit. A positive result prior to treatment will exclude the subject from study participation. The results of the UPT will be evaluated at each study center. If any subject has a positive UPT, a serum pregnancy test is required for confirmation.

If a female subject becomes pregnant while participating in the study, the investigator or site designee must complete a Pregnancy Report Notification Form provided by Revance or designee as soon as the pregnancy is confirmed (see Section 5.6).

#### **8.4.4. Injection Site Evaluation**

Injection sites will be evaluated at screening for signs of skin inflammation or active disease. The GL treatment areas will be evaluated at the Day 1 Visit (pre- and post-treatment) and at the Week 2 and 4 Visits. The FHL treatment areas will be evaluated at the Week 2 Visit (pre- and post-treatment) and at the Week 4 and 6 Visits. The assessment will be done as a global evaluation of the 5 injection sites for GL and 3 injection sites for FHL (Table 9). (Refer to Appendix 12 for additional information.)

**Table 9: Injection Site Evaluation**

Assessment Descriptor	Present?	
	Yes	No
Erythema		
Edema		
Burning or Stinging (sensation as described by subject)		
Itching (sensation as described by subject)		
Bruising		

If the subject answers yes to any of these items, it should be captured and recorded as an AE in the eCRF.

#### **8.4.5. Clinical Safety Laboratory Assessments**

As outlined in Table 10, non-fasting samples for hematology, chemistry, PT (screening only) and urinalysis will be collected at screening, Week 4 Visit, and Week 38 or Final Evaluation Visit.

■■■■■ Blood and urine specimens will be collected using applicable safety precautions and will be processed according to the central clinical laboratory's instructions. Urinalysis will be evaluated at the study center using supplies provided by Revance or designee.

**Table 10: Clinical Laboratory Tests**

Serum Chemistry	Hematology	Urinalysis	Additional Tests
Glucose	Hemoglobin	Specific gravity	Prothrombin time (PT)
Total bilirubin	Hematocrit	pH	(screening only)
Alanine aminotransferase	Leukocyte Count (total)	Glucose	UPT (WOCBP only)*
Aspartate aminotransferase	Leukocyte Count (differential)	Protein	[REDACTED]
Alkaline phosphatase	Red Blood Cell Count	Blood	[REDACTED]
Blood urea nitrogen	Platelet Count	Bilirubin	[REDACTED]
		Ketones	

\*If positive at timepoints after study treatment, confirm by serum pregnancy test

It is the investigator's responsibility to review the results of all laboratory tests as they become available. For each laboratory test result outside the reference range, the investigator must ascertain if the abnormal lab result is a clinically significant result for that individual subject. Likewise, if laboratory tests are taken at follow-up visits, the investigator must ascertain if this is an abnormal and clinically significant change from pretreatment for that individual subject. The investigator may repeat the laboratory test or request additional tests to verify the results of the original laboratory test.

The investigator must sign and date all written laboratory results (e.g., urinalysis, hematology, chemistry, PT, and pregnancy tests) and note Not Clinically Significant or Clinically Significant for each out of range laboratory value. If a laboratory value is determined to be a clinically significant result for that subject, this may be considered an AE.

[REDACTED]

[REDACTED]

[REDACTED].

[figure not shown]
[REDACTED] [REDACTED]

[REDACTED]

[REDACTED]

[REDACTED]

[REDACTED]

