**Safety Evaluations:**

- Clinical laboratory tests (hematology, serum chemistry, prothrombin time [PT], urinalysis)  
[REDACTED]  
[REDACTED]
- Injection site evaluation  
[REDACTED]
- Concomitant therapies/medications  
[REDACTED]
- Collection of adverse events (AEs)  
[REDACTED]
- Vital signs  
[REDACTED]
- Physical examination [REDACTED]

All TEAEs occurring during the study will be recorded and classified according to Medical Dictionary for Drug Regulatory Affairs (MedDRA) terminology. All reported TEAEs will be summarized, in terms of the number of subjects reporting events, system organ class, preferred term, severity, relationship to study drug, and severity. For summarization of event causality and severity, subjects will be counted only once within a system organ class or preferred term for a given event, using the event with the greatest relationship for causality and the highest severity. A summary of AEs leading to discontinuation will also be provided.

A by-subject listing of any SAEs will be provided and all SAEs will be summarized by severity and relationship to study treatment.

All AEs, including TEAEs, and SAEs will be summarized for the study overall and by dose group.

Clinical laboratory tests, including serum chemistry, hematology, PT (at the Screening Visit only), and urinalysis will be collected on Day 1, Week 4, and Week 38 or Final Evaluation Visit. [REDACTED]

[REDACTED]

[REDACTED]

[REDACTED]

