## 8.5. Adverse Events and Serious Adverse Events

### 8.5.1. Evaluation of Adverse Events and Serious Adverse Events

For this protocol, an **adverse event (AE)** is any untoward medical occurrence (e.g., sign, symptom, disease, syndrome, intercurrent illness, clinically significant abnormal laboratory finding, injury or accident) that emerges or worsens following administration of investigational product and until the end of study participation that may not necessarily have a causal relationship to the administration of the investigational product. An AE can therefore be any unfavorable and/or unintended sign (including a clinically significant abnormal laboratory result), symptom, or disease temporally associated with the use of an investigational product, if considered related to the investigational product. A treatment-emergent AE is one that occurs after any period of exposure to treatment.

Pre-existing conditions, which increase in frequency or severity or a change in nature as a consequence of an investigational product use will also be considered an adverse event.

An unexpected AE is an adverse reaction, the nature or severity of which is not consistent with the applicable product information (e.g., Investigator's Brochure for an unapproved investigational product or package insert/summary of product characteristics for an approved product).

Any change in the study safety evaluations, (e.g., vital signs, injection site [REDACTED] [REDACTED]) after GL and FHL treatment determined to be clinically significant by the investigator must be reported as an AE.

A **serious adverse event (SAE)** is any untoward medical occurrence that results in any of the following outcomes:

- Death
- Life-threatening, (i.e., the subject was, in the opinion of the investigator, at immediate risk of death from the event as it occurred. It does not apply to an AE that hypothetically might have caused death if it were more severe)
- Persistent or significant disability/incapacity or substantial disruption of the subject's ability to carry out normal life functions
  - Requires in-patient hospitalization or prolongs hospitalization (i.e., a prolonged hospitalization beyond the expected length of stay;

**NOTE:** Hospitalizations for **elective medical/surgical procedures**, scheduled treatments, or routine check-ups are **not SAEs** by this criterion)

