### **8.5.2. Assessment and Reporting Requirements**

The investigator will assess subjects after GL and FHL treatment and at each subsequent study visit for the occurrence of AEs. To avoid bias in eliciting AEs, subjects should be asked the following non-leading question: "How have you felt since your last visit?" All AEs (serious and non-serious) will be collected from signing of the ICF until the Final Evaluation Visit at each visit. Any AE reported by the subject must be recorded on the source documents and eCRFs.

All AEs will be collected from Day 1 until Week 38 or Final Evaluation Visit at the time points specified in the SOA (Section 1.3).

Medical occurrences that begin before the start of study intervention but after obtaining informed consent will be recorded on the Medical History/Current Medical Conditions section of the eCRF not the AE section.

All SAEs will be recorded and reported to Revance or designee immediately within 24 hours of their awareness of the event. All fatal or life-threatening SAEs should be telephoned to Revance or the designee's authorized representative as soon as the investigator learns of the event.

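### Protocol 8.4.5 and 8.5.1 give inconsistent rules for recording post-treatment clinically significant laboratory values as AEs

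*Protocol*

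**What the plan says.** The sentence in question stands in Protocol 8.4.5, in the text below Table 10. That text requires the investigator to sign each laboratory report and classify every out-of-range value as clinically significant or not. It then says: "If a laboratory value is determined to be a clinically significant result for that subject, this may be considered an AE".

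Protocol 8.5.1 deals with the same kind of finding in three sentences:

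- The first sentence of the AE definition gives laboratory findings as an example: "intercurrent illness, clinically significant abnormal laboratory finding, injury or accident) that emerges or worsens following administration of investigational product". It says that no causal relationship is needed.
- The second sentence says that an AE can be a sign (a clinically significant laboratory result is included), "symptom, or disease temporally associated with the use of an investigational product, if considered related to the investigational product".
- A later sentence covers changes in the study safety evaluations after GL and FHL treatment. Such a change, if "determined to be clinically significant by the investigator must be reported as an AE". The visible examples there are vital signs and injection site; the rest of the list is redacted.

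For vital signs, 8.4.2 says that a new or worse finding, "if judged clinically significant, should be recorded as an AE". For findings before treatment, 8.5.2 says: "Medical occurrences that begin before the start of study intervention but after obtaining informed consent will be recorded on the Medical History".

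**The concern.** A site that has just marked a laboratory value as clinically significant finds a permissive rule in 8.4.5. If it turns to 8.5.1 it finds one sentence that makes the value an AE and another that does so only if the value is considered related. Two sites could treat the same post-treatment value differently and each could point to the protocol.

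The incidence of TEAEs is the primary safety endpoint (Protocol 3; SAP 2.2.2). An event never entered on the AE form does not reach that count. The SAP rules for missing severity and missing relationship (3.3.1 and 5.8) cannot recover it, because they act only on events already recorded. The omission runs in one direction: it lowers TEAE incidence.

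**Working it through.** The plan gives no figure to reproduce here. The sample size is not based on power, and no calculation in the plan depends on this rule. The check is a comparison of the texts, with simple arithmetic for scale.

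**Step 1. Which values does the 8.4.5 sentence govern?** Under 8.4.5, hematology, chemistry and "urinalysis will be collected at screening, Week 4 Visit, and Week 38 or Final Evaluation Visit". Under 8.2.1, any abnormal screening result must be judged not clinically significant before enrollment. In a properly enrolled subject, a clinically significant scheduled result is therefore a Week 4 or final result that has appeared or worsened since screening. The exceptions are limited. The synopsis mentions a Day 1 sample, which could be taken before dosing, and 8.4.5 allows repeat or additional tests. In treated subjects the sentence mainly governs post-dose values.

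**Step 2. Apply each rule to such a value.**

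| Rule | Considered related | Considered unrelated |
|---|---|---|
| 8.4.5, text below Table 10 | optional | optional |
| 8.5.1, first sentence | AE | AE |
| 8.5.1, second sentence | can be an AE | falls outside the condition |
| 8.5.1, mandatory reporting sentence | must be reported, if it covers laboratory tests | must be reported, if it covers laboratory tests |

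The last row is uncertain because of the redaction. The synopsis does include laboratory tests among the safety evaluations ("Clinical laboratory tests (hematology, serum chemistry, prothrombin time [PT], urinalysis"), so coverage is plausible. The conflict does not depend on it, because the first sentence of 8.5.1 names laboratory findings expressly.

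**Step 3. Does another section settle it?** The protocol gives recording rules for other post-dose safety findings: vital signs (8.4.2), injection-site findings (Table 9) and physical findings that meet the AE definition (8.4.1). SAP 3.3.3, 3.3.6 and 3.3.7 repeat them. The visible text of SAP 3.3.4 and 6.6.4.1 has no rule for turning a clinically significant laboratory value into an AE. SAP 6.6.4.1 does list every clinically significant result, but a listing does not enter TEAE incidence.

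**Step 4. Size.** Let k be the number of subjects in a group of n whose only post-treatment event is such a laboratory value. TEAE incidence then differs between the two readings by k/n.

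- One cohort, n = 15, k = 1: 1/15 = 6.7 percentage points.
- All cohorts, n = 4 × 15 = 60, k = 1: 1/60 = 1.7 points.

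For comparison, the exact 95% confidence interval is 0 to 21.8% for 0/15 and 0.2 to 31.9% for 1/15. For 0/60 it is 0 to 6.0%, and for 1/60 it is 0.0 to 8.9%. One event moves the estimate by much less than its own uncertainty.

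The documents give no rate of such values. Under an assumed range of 2% to 10% of subjects, the expected number is 15 × 0.02 = 0.3 to 15 × 0.10 = 1.5 per cohort, and 60 × 0.02 = 1.2 to 60 × 0.10 = 6 overall. These count subjects with such a value. The number who move the incidence is smaller, because a subject with another TEAE is already counted.

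**The case against.** The best defence is that 8.4.5 does not define an AE and 8.5.1 does, so the permissive wording simply defers to the definition. Section 8.4.5 also covers screening samples, which cannot yield AEs, so a softer verb is right for some of the values it covers. This has some force, but Step 1 leaves few such values in treated subjects, and deferring to 8.5.1 does not help while 8.5.1 holds two different conditions.

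Four further points stand, and they limit the finding:

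- The mandatory sentence in 8.5.1 cannot be cited as clearly naming laboratory tests, because of the redaction.
- Clinical significance is the investigator's judgement under either section and would remain so after any edit.
- The laboratory data are not hidden. SAP 6.6.4.1 provides shift tables, changes from baseline, all out-of-range results with the significance call, and all clinically significant results. Protocol 8.5.5 requires clinically significant abnormal results at the final assessment to be followed. Only the TEAE count is exposed.
- Any positive item on the injection-site form is to be recorded as an AE, so some affected subjects may already count.

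A reader might infer more: that laboratory events enter the primary safety endpoint purely at each site's discretion, and that this could bias the comparison between doses. The documents do not support that. The protocol contradicts itself, with a rule that counts the event beside one that makes it optional, which is not the same as granting discretion. Nor does the visible text say how sites are spread over the cohorts, so there is no basis for expecting omissions to differ by dose.

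**Conclusion.** The point holds as an inconsistency in the text, wrong as written and minor in weight. For a clinically significant laboratory value that is new or worse after treatment, 8.4.5 leaves recording optional, the first sentence of 8.5.1 requires it to be counted, and the second sentence makes it depend on relatedness. Nothing in the visible SAP settles which applies.

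The effect is at most 6.7 points in a cohort or 1.7 points overall per affected subject. It assumes the planned 15 per cohort and 60 in total, and that the subject has no other TEAE. How many subjects would be affected is unknown. No planned analysis changes. What is at stake is whether all 4 sites count the same event in the same way.

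**What to change.** Make three changes together:

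1. In 8.4.5, replace the permissive sentence with wording such as: *A clinically significant laboratory result after GL treatment that is new or worse than the last pre-GL result must be recorded as an AE per Section 8.5.1. Pre-treatment findings are handled per Section 8.5.2.* The second part should point to the medical-history rule in 8.5.2.
2. In 8.5.1, delete the closing relatedness condition from the second sentence of the AE definition, so that it agrees with the first. Changing 8.4.5 alone would leave classification inconsistent.
3. Before database lock, check the SAP 6.6.4.1 listing of clinically significant results against the AE data, and query each post-GL result that is new or worse and has no matching AE.

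The cost is two protocol edits and one data check. TEAE incidence may come out slightly higher, within the per-subject limits above. Investigator judgement of clinical significance is left as it is.
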